5.5 Off Treatment Follow-up (30 days after stopping therapy)

Attempts will be made to follow-up with the patient in 30 days after the last dose of study drug. If a patient cannot return for the 30-day assessment and contact cannot be made due to disease progression, inability to return, hospice care, death, etc, this will not be considered a protocol deviation. Reporting to the IRB for deaths and other serious adverse events will be performed.

- Record concomitant medications.
- Adverse events will be assessed
- Optional blood draw for correlative studies

5.6 Crossover Phase

- At progression by RECIST, if they have not suffered an adverse event that would preclude them from continuing with systemic therapy and after the applicable washout period, of 2 weeks, patients who continue to meet the eligibility criteria will begin treatment with the remaining agent.

Note:

- At the discretion of the treating physician, the patient may continue on their 1st-line agent if the treating physician believes the patient is benefitting, despite progression by RECIST.
 - Patient may start their 2nd-line therapy within 2 weeks from the last dose of the agent given in 1st-line, if felt indicated by the treating physician.
 - Patients who develop progressive disease while receiving the 1st-line agent may receive radiation therapy or undergo surgery if indicated and continue to receive treatment on protocol, as long as the 2nd-line agent is commenced within 8 weeks from discontinuation of the 1st-line agent.
- For the cross-over stage of the study, patients will repeat the schedule of assessments as provided in the study calendar and section 5.4. Cardiovascular assessments will only be repeated if more than 24 weeks from the previous exams and only for those who'll be receiving pazopanib. A MRI/CT of the brain will be performed at crossover to rule out any progression before the start of crossover therapy at the discretion of the physician.
 - Screening blood work must have been performed within the past 14 days before starting the new treatment.
 - Optional blood draws will continue the same schedule as indicated in the study calendar.

5.7 Long-Term Follow-up

Patients will be followed for overall survival every 3 months after removal from final study therapy. Follow-up will consist of a phone call, e-mail correspondence or medical record review.

5.8 Supportive Care

The use of concurrent medications and blood products will be left to the discretion of the treating physician and should follow established guidelines.

5.9 Duration of Therapy

Patients may continue therapy until progressive disease by RECIST criteria or until other criteria for removal (Section 12) has been met.

6.0 DOSING DELAYS/DOSE MODIFICATIONS

6.1 General Guidelines

Doses will be delayed or reduced for clinically significant hematologic, renal, and other toxicities that are related to pazopanib or temsirolimus, as determined by the investigators at MD Anderson. All toxicity will be assessed using the NCI CTC version 4.0. Recovery from any toxicity to at least grade 1 or baseline as outlined below must occur prior to re-initiating therapy with agent responsible for the toxicity. Treatment with the same agent will resume as soon as possible with the appropriate dose reductions. Patients receiving treatment who experience an adverse event that necessitates its interruption and a delay of ≥ 6 weeks in its re-initiation will discontinue it and come off protocol. In all cases, patients, who are withdrawn from the study due to adverse event(s), must be followed until resolution of the adverse event(s) or start of new treatment. If a patient experiences several toxicities leading to conflicting recommendations, the recommended dose adjustment reducing the dose to the lowest level will be used. The dose of any study drug may be re-escalated to a higher level following discussion with the principal investigator. All dose modifications will follow predefined dose levels.

Patients who require any emergency intervention (e.g. for appendectomy or cholecystectomy because of trauma complications) or who require a procedure (e.g. Kyphoplasty/vertebroplasty) may remain on trial, even if administration of the targeted agent is interrupted, as long as the targeted agent is resumed within 6 weeks from date of interruption.

Pulmonary Embolism

Patients who are incidentally discovered on CT scan imaging to have pulmonary embolism may receive anticoagulation and continue treatment on protocol at the discretion of the treating physician.

6.1.1 Pazopanib Dose Modifications

Dose Modifications for Pazopanib Associated Toxicity

Toxicity	Grade 1	Grade 2	Grade 3	Grade 4
Non-hematological	Continue at the same dose level	Continue at the same dose level	Withhold dose until toxicity is grade \leq 1 or has returned to baseline, then resume treatment with the dose reduced by 1 level	Withhold dose until toxicity is grade \leq 1 or has returned to baseline, then resume treatment with the dose reduced by 1 level
Hematological	Continue at the same dose level	Continue at the same dose level	Withhold dose until toxicity is grade \leq 1 or has returned to baseline, then resume treatment at the same dose level	Withhold dose until toxicity is grade \leq 1 or has returned to baseline, then resume treatment at the same dose level

Dose Level	Pazopanib
0	800 mg oral Daily
-1	600 mg oral Daily
-2	400 mg oral Daily

6.1.1.1 Guidelines for Management of Treatment Emergent Hepatotoxicity

In the event of treatment emergent hepatotoxicity, potential contributing factors such as concomitant medications, viral hepatitis, choledocholithiasis, and hepatic metastases should be investigated. Concomitant medications known to be hepatotoxic which may be contributing to liver dysfunction should be discontinued or replaced with alternative medications to allow for recovery of liver function. As generally understood, ALT $>3x$ ULN and concomitant bilirubin $\geq 2.0x$ ULN ($>35\%$ direct bilirubin), in the absence of elevated alkaline phosphatase or biliary injury, suggests significant liver injury. The table below provides guidelines for hepatotoxicity monitoring.

Event	Dose Modification Algorithms
(A). ALT $\leq 3.0 x$ ULN	Continue study treatment at current dose with LFTs monitored as per protocol.

(B). ALT >3.0 x ULN to ≤8.0 x ULN without bilirubin elevation (defined as total bilirubin <2.0 x ULN or direct bilirubin ≤35%) and without hypersensitivity symptoms (e.g., fever, rash)
	
Liver Event Monitoring Criteria:
 
(1) Continue study treatment at current dose levels.
 
(2) Monitor subject closely for clinical signs and symptoms; perform full panel LFTs once weekly or more frequently if clinically indicated until ALT/AST is reduced to Grade 1.


(C). ALT >8.0 x ULN without bilirubin elevation (defined as total bilirubin <2.0 x ULN or direct bilirubin ≤35%) and without hypersensitivity symptoms (e.g., fever, rash)
	
1st occurrence – Liver Event Interruption Criteria:
 
(1) Interrupt treatment until toxicity resolves to ≤Grade 1 or baseline. Repeat liver chemistries within 24 to 72 hours.
 
(2) Monitor subject closely for clinical signs and symptoms; perform full panel LFTs once weekly or more frequently if clinically indicated until ALT is reduced to Grade 1.
 
(4) If the subject is benefiting from the study treatment, consider re-challenge. Re-treatment may be considered at a dose of 400 mg once daily and with weekly serum liver tests x 8 weeks, if ALL following criteria are met:
 
 - ALT reduced to Grade 1 - Total bilirubin <1.5 x ULN or direct bilirubin ≤35% - No hypersensitivity signs or symptoms - Subject is benefiting from therapy. 
Recurrence – Liver Event Stopping Criteria:
 
Discontinue pazopanib permanently and monitor subject closely for clinical signs and symptoms; perform full panel LFTs once weekly or more frequently if clinically indicated until ALT is reduced to Grade 1.

(D). ALT >3.0 x ULN with concomitant elevation in bilirubin² (defined as total bilirubin ≥2.0 x ULN; with direct bilirubin >35%) or with hypersensitivity symptoms (e.g., fever, rash)
	
Liver Event Stopping Criteria:
 
(1) Discontinue treatment immediately, and report the event to Novartis as an SAE within 24 hours of learning of its occurrence. Repeat LFTs within 24 hours.
 
(2) Consult a gastroenterologist / hepatologist, and perform the following assessments to identify potential co-factors:
 
 - Eosinophil count - Viral serology for hepatitis A, B, C and E, cytomegalovirus, Epstein-Barr virus (IgM antibody, heterophile antibody, or monospot testing) - Anti-nuclear antibody, anti-smooth muscle antibody, anti-mitochondrial antibody - Serum creatinine phosphokinase for possible muscle injury caused LFT elevation

	
- Liver imaging
 
(3) Monitor subject closely for clinical signs and symptoms; record the appearance or worsening of clinical symptoms of hepatitis, or hypersensitivity, such as fatigue, nausea, vomiting, right upper quadrant pain or tenderness, fever rash or eosinophilia as relevant on the AE report form. Perform full panel LFTs weekly or more frequently if clinically indicated until LFTs are reduced to Grade 1.

For isolated total bilirubin elevation without concurrent ALT increases (defined as ALT <3 X ULN).	
(1) Isolated hyperbilirubinemia (i.e., in the absence of elevated ALT or other signs/symptoms of liver injury) does not require dose modification. Pazopanib inhibits UGT1A1 and OATP1B1, which can cause elevation of indirect (unconjugated) bilirubin in the absence of liver injury.
 
(2) If bilirubin is >2 x ULN in the absence of ALT elevation, fractionation of bilirubin elevation should be performed. If the bilirubin is predominantly indirect (unconjugated), continue pazopanib at the same dose. If bilirubin is >35% direct (conjugated), further evaluation for underlying cause of cholestasis should be performed.

1. Full panel LFTs include: AST, ALT, alkaline phosphatase, , and total bilirubin.
2. Serum bilirubin fractionation should be performed if testing is available. If testing is unavailable and a subject meets the criterion of total bilirubin ≥ 2.0 x ULN, then the event should be promptly reported as defined.
3. When a liver chemistry event meets the Liver Event Interruption Criteria, or Liver Event Stopping Criteria, blood samples should be obtained for clinical laboratory testing.

Abbreviations: ALT alanine aminotransferase; AST aspartate aminotransferase; LFT liver function tests; SAE serious adverse event; ULN upper limit of normal.

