Pharmacokinetic data from patients with normal hepatic function (n = 12) and moderate (n = 7) hepatic impairment indicate that pazopanib clearance was decreased by 50% in those with moderate hepatic impairment. The maximum tolerated pazopanib dose in

patients with moderate hepatic impairment is 200 mg once daily. There are no data on patients with mild or severe hepatic impairment.

Drug Interactions: Coadministration of oral pazopanib with CYP3A4 inhibitors has resulted in increased plasma pazopanib concentrations. Concurrent administration of a single dose of pazopanib eye drops with the strong CYP3A4 inhibitor and Pgp inhibitor, ketoconazole, in healthy volunteers resulted in 220% and 150% increase in mean AUC(0-t) and Cmax values, respectively.

Administration of 1,500 mg lapatinib, a substrate and weak inhibitor of CYP3A4, Pgp, and BCRP, with 800 mg pazopanib resulted in an approximately 50% to 60% increase in mean pazopanib AUC(0-24) and Cmax compared to administration of 800 mg pazopanib alone.

In vitro studies with human liver microsomes showed that pazopanib inhibited the activities of CYP enzymes 1A2, 3A4, 2B6, 2C8, 2C9, 2C19, 2D6, and 2E1. Potential induction of human CYP3A4 was demonstrated in an in vitro human PXR assay. Clinical pharmacology studies, using pazopanib 800 mg once daily, have demonstrated that pazopanib does not have a clinically relevant effect on the pharmacokinetics of caffeine (CYP1A2 probe substrate), warfarin (CYP2C9 probe substrate), or omeprazole (CYP2C19 probe substrate) in cancer patients. Pazopanib resulted in an increase of approximately 30% in the mean AUC and Cmax of midazolam (CYP3A4 probe substrate) and increases of 33% to 64% in the ratio of dextromethorphan to dextrorphan concentrations in the urine after oral administration of dextromethorphan (CYP2D6 probe substrate). Coadministration of pazopanib 800 mg once daily and paclitaxel 80 mg/m² (CYP3A4 and CYP2C8 substrate) once weekly resulted in a mean increase of 26% and 31% in paclitaxel AUC and Cmax, respectively.

In vitro studies also showed that pazopanib inhibits UGT1A1 and OATP1B1 with IC50s of 1.2 and 0.79 microM, respectively. Pazopanib may increase concentrations of drugs eliminated by UGT1A1 and OATP1B1.

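### Pazopanib with isolated conjugated bilirubin above 2 x ULN (ALT below 3 x ULN): the protocol asks for a work-up but sets no hold or dose cap, although it reports a 200 mg maximum tolerated dose in moderate hepatic impairment

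*Combined protocol and SAP*

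**What the plan says.** **Dose levels.** Section 6.1.1 lists three pazopanib levels: 800, 600 and, lowest, "400 mg oral Daily". Section 6.1 adds: "All dose modifications will follow predefined dose levels".

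**Isolated bilirubin elevation (last row of the 6.1.1.1 table, ALT below 3 x ULN).** Item 1 says that isolated hyperbilirubinemia, without raised ALT or other evidence of liver injury, "does not require dose modification". Item 2 asks for fractionation above 2 x ULN. If the bilirubin is mainly indirect, pazopanib continues at the same dose. If more than 35% is direct, "further evaluation for underlying cause of cholestasis should be performed". No dose instruction follows in that branch.

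**Neighbouring rows.** Row A (ALT up to 3 x ULN) continues treatment at the current dose and carries no bilirubin condition. Row C allows re-challenge, at 400 mg, only if bilirubin is below 1.5 x ULN or the direct share is 35% or less, among other conditions. Row D (ALT above 3 x ULN with bilirubin at or above 2 x ULN and more than 35% direct) stops the drug at once.

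**Hepatic impairment.** Section 3.1.4 reports that "pazopanib clearance was decreased by 50% in those with moderate hepatic impairment" and that the maximum tolerated dose in "patients with moderate hepatic impairment is 200 mg once daily". Section 6.1.2.1 has a hepatic-impairment dose rule for temsirolimus. Section 6 has none for pazopanib.

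**The concern.** The table gives a dose instruction when raised bilirubin is mainly indirect, which it attributes to enzyme and transporter inhibition without liver injury. It gives none when the bilirubin is conjugated, the case for which it suspects cholestasis. A physician following the rules as written can therefore leave a cholestatic patient on 800 mg while the cause is sought, and afterwards.

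The protocol's own pharmacology makes that uncomfortable, because it reports a much lower tolerated dose when hepatic function is moderately impaired. That figure is used nowhere in the dose rules, and a physician who wanted 200 mg would find no defined level for it.

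The matter is patient safety in the experimental arm and after crossover to pazopanib. It does not touch the sample size, the PFS comparison or the error rates.

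**Working it through.** The plan gives no figure to reproduce. The check sets the rules side by side and then takes dose ratios.

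**Step 1. Which rule applies to a patient with ALT below 3 x ULN, bilirubin above 2 x ULN and more than 35% direct?**

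| Rule | Applies? | Instruction |
|---|---|---|
| 6.1.1.1 row A | Yes, on ALT alone | Continue at current dose |
| 6.1.1.1 rows B, C | No (ALT too low) | – |
| 6.1.1.1 row D | No (needs ALT above 3 x ULN) | – |
| 6.1.1.1 isolated bilirubin, item 2 | Yes | Work-up only |
| 6.1.1 general table | Only at Grade 3–4 | Withhold, "then resume treatment with the dose reduced by 1 level" |
| 6.1.2.1 | No (temsirolimus only) | – |

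The general table is not a reliable backstop. Section 6.1 limits dose changes to hematologic, renal and "other toxicities that are related to pazopanib or temsirolimus", so impairment caused by liver metastases or obstruction falls outside it. The protocol prints no bilirubin grade cut-offs. Where the table does act, one step down from 800 mg is 600 mg.

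**Step 2. Internal consistency.** After an ALT event, row C withholds even 400 mg while bilirubin is 1.5 x ULN or more and over 35% direct. The isolated row sets no limit at 800 mg for a patient with bilirubin above 2 x ULN and over 35% direct. Rows B, C and D also require at least weekly liver tests during the event. The isolated row adds none, and scheduled pazopanib chemistry (5.4) moves from every 2 weeks for the first 8 weeks to every 8 weeks twice and then every 16 weeks.

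**Step 3. Can such patients arise?** Entry requires bilirubin of at most 1.5 mg/dl (4.1, criterion 6), and crossover requires continued eligibility (5.6). The issue is therefore liver dysfunction that emerges on treatment. Patients with liver metastases are eligible.

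**Step 4. Dose ratios, if the patient has moderate impairment.** Inputs: maximum tolerated dose 200 mg and clearance multiplied by 0.5 (3.1.4); levels 800, 600 and 400 mg (6.1.1). Ratio = dose / 200. Relative exposure = dose / (0.5 × 800), with 800 mg at normal clearance as the reference. This assumes AUC proportional to dose from 200 to 800 mg.

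| Dose | Ratio to 200 mg | Relative exposure |
|---|---|---|
| 800 mg | 800/200 = 4 | 800/400 = 2.0 |
| 600 mg | 600/200 = 3 | 600/400 = 1.5 |
| 400 mg | 400/200 = 2 | 400/400 = 1.0 |
| 200 mg | 200/200 = 1 | 200/400 = 0.5 |

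The supplied tablet is 200 mg (3.1.1) and must not be crushed (3.1.4). With whole tablets, 200 mg is the only once-daily dose below 400 mg.

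**The case against.** The strongest reply is that physicians are not trapped.

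- **Stopping routes.** Treatment may stop for prohibitive toxicity (5.2) or for intercurrent illness or progression (Section 12), and a delay of 6 weeks or more for an adverse event takes the patient off protocol (6.1). This stands, but these are discretionary or late exits. None triggers a hold or sets a dose in this branch.
- **The exemption is conditional.** Item 1 exempts only patients without other evidence of liver injury, and the conjugated branch does not itself say to continue. This also stands. It leaves the dose open, and row A then fills the silence with continuation.
- **The label.** Sections 3.1.6 and 6.2 point to the product label, which is not among the documents. Whether it covers this case is unknown. No pointer adds a level to 6.1.1.
- **400 mg restores normal exposure.** It does on the arithmetic above, but the tolerated dose reported in 3.1.4 is half of that.

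Three stronger readings are tempting and not supported:

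- A reader might infer that all conjugated bilirubin above 2 x ULN gets a work-up only. Row D contradicts this when ALT exceeds 3 x ULN. For the same reason, the entry allowance of AST or ALT up to 5 x ULN with liver metastases is weak evidence for this row, since a patient whose ALT is above 3 x ULN goes to row D.
- A reader might infer that the protocol prescribes 4 times a known safe limit. That requires equating this laboratory pattern with moderate impairment, which the documents never do.
- A reader might treat the missing level below 400 mg as an equal hazard with strong CYP3A4 inhibitors (6.1.1.3), uncontrolled hypertension (6.1.1.2 item 2) or a repeat Grade 3–4 event (6.1.1). Those are mostly gaps in wording, which a physician would settle by stopping.

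**Conclusion.** The concern holds for one branch: ALT below 3 x ULN with bilirubin above 2 x ULN that is more than 35% direct. No rule there holds pazopanib or caps its dose, row A literally continues it, and the protocol's own figure for moderate hepatic impairment is unused. If the patient is moderately impaired, the defined levels are 2 to 4 times the reported maximum tolerated dose.

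That size rests on two assumptions: that the pattern represents moderate impairment, which 3.1.4 does not define, and that the interim result carries over to impairment arising on treatment. The interim data include 7 patients with moderate impairment, and the study's starting doses were assigned by hepatic function. The exposure ratios further assume dose proportionality. The absence of a dose rule depends on none of these.

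The documents give no rate for this event and no crossover rate, so the number of patients affected cannot be derived. This is a safety clarification that should be made. It is not a flaw in the trial's inference.

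**What to change.** **Main change, in the isolated bilirubin row of 6.1.1.1 and as a stated exception to row A.** For bilirubin above 2 x ULN with more than 35% direct:

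- Hold pazopanib during the work-up.
- Resume at a predefined level only when bilirubin is below 1.5 x ULN or the direct share is 35% or less, which is row C's own bilirubin criterion.
- If moderate impairment persists, with the cut-off written into the protocol, give no more than 200 mg daily as a level defined for this use, or discontinue.
- Discontinue in severe impairment. Section 3.1.4 reports no data there, and the study it cites started such patients at 100 mg.
- Do not apply the 200 mg cap to mild impairment, where the same study started at 400 mg.

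**Minor clarification.** State in 6.1.1 that a patient at 400 mg who needs a further reduction discontinues pazopanib (or drops to 200 mg), and align 6.1.1.2 and 6.1.1.3 with that choice. Rows C and D and the rule for indirect bilirubin stay as they are.

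**Cost.** A few sentences and, if 200 mg is chosen, one dose-level line. The tablet strength is already supplied, and the sample size and endpoints do not change. The downside is that a few patients with cholestasis receive less drug or stop earlier.

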6.1.1.2 Guidelines for Management of Treatment Emergent Hypertension

Hypertension Grade of Event per MDACC guidelines	Management/ Next Dose
Grade 1	Consider increased BP monitoring
Grade 2 asymptomatic and diastolic BP < 110 mm Hg	Begin anti-hypertensive therapy and continue agent

requiring more than 3 antihypertensive medications.	
Grade 2 symptomatic/persistent OR diastolic BP \geq 110 mm Hg OR grade 3	1. Agent should be held until symptoms resolve and diastolic BP \leq 100 mm Hg; also treat patient with anti-hypertensives and when agent is restarted, reduce by 1 dose level. Following discussion with the PI, determination to continue with same dose or reduce by 1 level may be made. 2. If diastolic BP not controlled (\leq 100) on maximal medical therapy (as defined as more than 3 antihypertensive medications), reduce one dose level
Grade 4	Discontinue the offending agent and remove patient from

MDACC Hypertension definitions:

Grade 1: asymptomatic, transient (< 24 hours) increase > 20 mmHg (diastolic) or to >140/90 if previously WNL; intervention not indicated

Grade 2: recurrent or persistent (>24 hours) or symptomatic increase > 20 mmHg (diastolic) or to >140/90 if previously WNL; monotherapy may be indicated.

Grade 3: requiring multiple antihypertensive agents or more intensive therapy than previously

Grade 4: life-threatening (e.g., hypertensive crisis)

6.1.1.3 Concomitant Strong CYP3A4 Inhibitors:

The concomitant use of strong CYP3A4 inhibitors (e.g., ketoconazole, ritonavir, clarithromycin) may increase pazopanib concentrations and should be avoided. If coadministration of a strong CYP3A4 inhibitor is warranted, reduce the dose of pazopanib to 400 mg. Further dose reductions may be needed if adverse effects occur during therapy. This dose is predicted to adjust the pazopanib AUC to the range observed without inhibitors. However, there are no clinical data with this dose adjustment in patients receiving strong CYP3A4 inhibitors.

6.1.1.4 12-Lead Electrocardiogram

In clinical studies with pazopanib, events of QT_cB prolongation have occurred. For patients receiving pazopanib a 12-lead ECG will be obtained at Screening/Baseline and again at Cycle 2 Day 1. If QT_cB is normal, patients will have an ECG every 16 weeks thereafter. Prior to each ECG test, the subject should be at rest for approximately 10 minutes.

If the QT_cB interval at any ECG during treatment is \geq 500 msec, study drug will be held and the ECG should be repeated within 7 days and, if the QT_cB interval remains

≥ 500 msec, the subject should be removed from the study. The ECG can be performed at an outside facility with results sent to MDACC.

Additionally, if the QT_cB interval is increased by 60 msec or more from baseline, but the QT_cB interval remains at < 500 msec, an ECG should be repeated within 7 days. If the repeat ECG again shows a ≥ 60 msec increase in the QT_cB interval from baseline, consideration should be given to removing the subject from the study or increasing monitoring, after discussion with the principal investigator.

NOTE: If the QT_cB prolongation > 500 msec is clearly and causally associated with an underlying situation that is clearly reversible (e.g., a subject with severe diarrhea and hypokalemia with QT_cB prolongation that resolves once the diarrhea improves and potassium is corrected), then the subject may restart study drug once the underlying situation has been corrected (e.g., electrolytes supplemented), the QT_cB interval prolongation has resolved.

